1.3 Rationale for the Proposed Study

RP is an incurable blinding disease caused by death of first rod, then cone, photoreceptors in the retina. Photoreceptors are specialized nerve cells essential for vision. Once photoreceptors are lost, they do not regenerate. Therefore, when all rods and cones have died, the patient is left completely blind. Preclinical studies demonstrated that transplantation of retinal progenitor cells into the eye can result in both photoreceptor replacement and significant slowing of host photoreceptor loss¹⁰. Thus, the primary goal of jCell therapy is to preserve, and potentially improve, vision by intervening in the disease at a time when dystrophic host photoreceptors can be protected and reactivated.

There are only extremely limited human data available for hRPC that may not be entirely representative of the current jCell investigational product but are considered supportive. In an extremely limited non-US pilot group of 3 legally blind patients that received a single hRPC injection of 500,000 cells each in one eye, there were no surgical complications other than 1 transient sterile anterior chamber reaction that resolved with standard steroid drops. There were no signs of immune rejection, without immunosuppression, and despite the transient anterior inflammation in one patient, there was no clinically evident cell

proliferation in vivo based on all examinations (slit-lamp, 30D lens, B scan, fundus photos, etc.) and no tumor formation was detected during follow up to 8 months.

All three patients experienced some improvement in visual acuity and one patient also showed evidence of improvement in visual field area and ERG. These limited results of hRPC administration reported in these three patients are encouraging but are interpreted with caution due to the extremely small number of subjects.

The study population proposed herein is limited to adults since the severe stage of the degeneration of the type described typically occurs in adulthood. In non-syndromic RP, the retina is the isolated disease focus, without involvement of other organs or systems that might contribute to adverse events. The criterion for baseline visual acuity in the range of 20/200 to "hand motions" (HM) in the initial cohort is chosen because in this range, the disease is advanced and visually disabling, yet some residual photoreceptors are still present to be acted upon therapeutically. In the second cohort, patients will have best corrected visual acuity (BCVA) of 20/40 or worse and visual fields of 10 degrees or less. This level of vision is significantly impaired, yet better than the initial cohort, thereby allowing greater potential for macular cone rescue.

2.0 **OBJECTIVES**

2.1 Primary Objective

The primary objective is to evaluate the safety and tolerability of jCell injection in adult subjects with non-syndromic RP.

2.2 Secondary Objectives

The secondary objectives of the study are to monitor ocular function over a 12 month period following a single injection of hRPC (jCell) to evaluate the potential therapeutic response in subjects with RP.

3.0 STUDY DESIGN

This is a prospective, multicenter, open-label, single-arm, Phase I/II trial of hRPC (jCell) for the treatment of retinitis pigmentosa (RP). Study subjects will be screened for eligibility, informed consent obtained, baseline studies of primary and exploratory endpoints performed. Then the subjects will be enrolled into one of two cohorts. Cohorts will be treated consecutively for each dose level, with review of safety data at scheduled intervals. That is, once a dose level is completed in Cohort 1, the enrollment of Cohort 2 subjects into that dose level can be initiated assuming no safety issues in Cohort 1 subjects at that dose level. Subjects will be entered into a treatment cohort based upon the order of enrollment at each of the study sites. Subjects in both cohorts will be followed for one year under this protocol and will be encouraged to participate in a follow-on study of long term safety and tolerability for an additional two years at study completion.

3.1 Study Population

3.1.1 Cohort One

Up to 14 subjects will be enrolled into Cohort 1. Subjects in Cohort 1 must have BCVA no better than 20/200 and no worse than Hand Motions (HM, i.e. the patient can distinguish horizontal from vertical hand motions at 1 foot). The first four subjects in Cohort 1 will receive an intravitreal injection of 0.5 x 10^6 hRPC (50 μ L volume) into the eye with the worst visual acuity; only one eye will be injected. The procedure does not require in-patient hospitalization and can be done under topical anesthesia. Subjects will be monitored closely following injection for 60 minutes prior to being released home on the day of treatment, based on intraocular pressure <30mm Hg and vital signs returned to pre-injection. Patients will be treated with ophthalmic corticosteroid eye drops to minimize any inflammation from injection for up to 14 days (including tapering schedule). There will be a minimum four week interval between the treatment of the first and second subjects in this cohort, with follow up at 1, 2, 3, 7, 14 and 21 days post-injection by the study investigator to confirm no serious injection related AEs have occurred for subject #1 prior to treatment of subject #2. Subsequent cohort 1 subjects at the same dose level will be spaced at least one week apart (subjects 2, 3 and 4), with follow up at 1, 2 and 3 days post-injection for each subject prior to treatment of the next subject at that dose level. All subjects will receive injection of cells into the eye with the poorest visual acuity. Following at least one week of safety observations for the last study subject at the lower dose level, safety and tolerability data will be reviewed by the DSMB. Assuming no unexpected safety issues and with DSMB recommendation, an additional 4 subjects will be enrolled in Cohort 1 and treated at the second dose level, 1.0 x 10⁶ hRPC. Treatment will be similar to the first four subjects, i.e. intravitreal injection under topical anesthesia with treatment of the first two subjects separated by at least 4 weeks and subsequent subjects in this cohort (subject 6, 7 and 8) spaced at least one week apart. Following at least one week of safety observation for the last Cohort 1 subject, safety and tolerability data will be reviewed by the DSMB prior to initiation of Cohort 2.

Following completion of DSMB review of the first 8 subjects in Cohort 1 (dose levels 0.5 x 10^6 and 1x 10^6 hRPC), an additional three subjects may be enrolled into Cohort 1 and treated at the third dose level, 2 x 10^6 hRPC (50µL volume). Treatment will be administered as described above for the first two dose levels, with all subjects spaced at least a week apart. Following at least one week of safety observations for the last study subject at the 2 x 10^6 hRPC dose level, safety and tolerability data will be reviewed by the DSMB. Assuming no unexpected safety issues and with DSMB recommendation, an additional 3 subjects may be enrolled into Cohort 1 for treatment at the highest dose level, 3.0×10^6 hRPC (50 µL volume). Treatment will be administered as described above for the first two dose levels, with all subjects spaced at least a week apart.

3.1.2 Cohort Two

Up to 14 subjects will be enrolled into Cohort 2, following completion of Cohort 1 and review of Cohort 1 safety and tolerability data by the DSMB at the relevant dose level. Subjects in Cohort 2 must have BCVA no better than 20/40 and no worse than 20/200. The first four subjects in Cohort 2 will receive an intravitreal injection of 0.5×10^6 hRPC into the eye with the worst visual acuity; only one eye will be injected. As noted above, the procedure can be done under topical anesthesia. Subjects will be monitored closely following injection for 60 minutes prior to being released home on the day of treatment, based on intraocular pressure <30mm Hg and vital signs returned to pre-injection. Patients will be treated with ophthalmic corticosteroid eye drops to minimize any inflammation from injection for up to 14 days (including tapering schedule). Assuming no unexpected safety issues in the low dose group, an additional 4 subjects will be enrolled in Cohort 2 and treated at the second dose level, 1.0×10^6 hRPC.

Once the first two dose levels are completed in Cohort 2, and following the review of safety data from Cohort 1 subjects who were treated at the third dose level (2.0×10^6 hRPC), three additional subjects may be enrolled into Cohort 2 and treated at the 2×10^6 hRPC dose level. Following this and assuming no unexpected safety issues in the Cohort 1 subjects at the 3×10^6 dose level, three additional subjects may be enrolled into Cohort 2 and treated at this highest dose level. Assuming safety and tolerability data from the relevant dose levels in Cohort 1 are acceptable, there will be no minimum interval between treatment of subjects in Cohort 2.

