The investigational product (jCell) is a live suspension of $0.5-3.0 \times 10^6$ human retinal progenitor cells (hRPC) suspended in clinical grade medium. The hRPC are of allogeneic human fetal origin. Study subjects will receive a single dose of either 0.5, 1.0, 2.0, 3.0 x 10^6 jCell as an intravitreal injection under topical anesthesia into the eye with the worst visual acuity.

Duration of treatment:

Treatment with jCell consists of a single intravitreal injection. The injection procedure itself takes approximately 2 minutes. Patients will be released to home on the day of injection. Study subjects will be followed for one year post-injection under this protocol with a separate protocol planned for two additional years of long term follow up.

Criteria for Evaluation:

Efficacy:

Efficacy will be assessed based on a series of ophthmalogic assessments at specified timepoints, including best corrected visual acuity (BCVA), spectral domain optical coherence tomography (OCT), electroretinogram (ECG), visual field testing (where appropriate), fluorescein angiography, autofluorescence and a visual quality of life

NAME OF COMPANY: jCyte, Inc	SUMMARY TABLE	(For national Authority Use Only)
NAME OF FINISHED PRODUCT: iCell	Volume:	
NAME OF ACTIVE INGREDIENT:	Page:	
human retinal progenitor cells	Reference:	

questionaire (VFQ-25). In addition, several low vision assessment tools may be explored in subsets of subjects in order to better understand which assessments may be most useful for this type of treatment approach. None of these assessments are invasive.

Safety:

Safety will be assessed on an ongoing basis by adverse events, identification of dose-limiting toxicities (if any), physical examinations and vital signs, clinical laboratory values, and anti-drug antibodies. In addition, specific ophthalmalogic tests to monitor safety will be performed, including slit lamp and fundus examiniation, B-scans and intraocular pressure (IOP). Additional ophthalmalogic tests described above will also contribute to safety monitoring.

Clinical safety data will be reviewed on an ongoing basis. Safety data will undergo formal review by a DSMB following completion of each dose level 1 in Cohort 1 before initiation of the next dose level in Cohort 1, and before the initiation of the same dose level in Cohorty 2.

Statistical methods:

Background and demograhic data will be summarized for all subjects using descriptive statistics.

Efficacy:

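### Neither gate for Cohort 2's steps to 2.0 and 3.0 million cells requires a scheduled review of Cohort 2's own safety data

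*Protocol*

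**What the plan says.** Protocol 3.1.2 sets three upward steps for Cohort 2.

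- **To 1.0 million:** "Assuming no unexpected safety issues in the low dose group, an additional 4 subjects will be enrolled in Cohort 2".
- **To 2.0 million:** the first two levels must be completed in Cohort 2, and the step comes "following the review of safety data from Cohort 1 subjects who were treated at the third dose level".
- **To 3.0 million:** "Following this and assuming no unexpected safety issues in the Cohort 1 subjects at the" 3 million level.

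The synopsis carries the same conditions, and SAP section 3 restates them.

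The surrounding text also points to Cohort 1. The opening of 3.1.2 places Cohort 2 enrolment after "review of Cohort 1 safety and tolerability data by the DSMB at the relevant dose level". Section 3.0 says that enrolment of Cohort 2 at a level "can be initiated assuming no safety issues in Cohort 1 subjects at that dose level". The synopsis, under safety evaluation, states: "Safety data will undergo formal review by a DSMB following completion of each dose level 1 in Cohort 1", before the next Cohort 1 level "and before the initiation of the same dose level in Cohorty 2". Provided the Cohort 1 data are acceptable, "there will be no minimum interval between treatment of subjects in Cohort 2".

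**The concern.** The two highest Cohort 2 steps can be taken, exactly as written, without a scheduled look at Cohort 2 eyes. The word used for Cohort 2's first two levels is completion, which carries no follow-up time and no data review. This departs from the protocol's own pattern. Cohort 1's steps to 1.0 and 3.0 million follow DSMB review and recommendation (3.1.1), and Cohort 2's step to 1.0 million looks at the low-dose group.

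Cohort 1 data at the same dose are relevant but are not a full substitute. Cohort 2 has acuity of 20/40 to 20/200, against 20/200 to hand motions in Cohort 1, so it has more vision to lose. Treatment-related loss of BCVA is a stated safety criterion (3.2.2). It is also harder to see in Cohort 1: Protocol 3.2.1 concedes that BCVA performs poorly at very low vision, and SAP 9.1 scores counting-fingers and hand-motions eyes as zero letters, so such an eye cannot record a letter loss. Experience of Cohort 2 eyes at lower doses is the direct evidence on tolerability in that vision range.

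**Working it through.** **Plan's own figure.** Level sizes from Protocol 3.1.2 are 4, 4, 3 and 3, so 4 + 4 + 3 + 3 = 14, which matches the stated Cohort 2 maximum.

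**Subjects treated before each step, at full enrolment.**

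- Cohort 2 before 2.0 million: 4 + 4 = 8. Before 3.0 million: 4 + 4 + 3 = 11.
- The 4 low-dose subjects are considered at the 1.0 million step. Those under no Cohort 2 gate are 8 − 4 = 4 and 11 − 4 = 7.
- Cohort 1 by then: at least 4 + 4 + 3 = 11 before Cohort 2's 2.0 million step, and 14 before its 3.0 million step.

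**What the suspension rule leaves open.** The synopsis suspends the study for two or more patients with the same grade 3 event, or one with a grade 4 event. One grade 3 case, or any number of grade 2 cases, does not trigger it.

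**Illustration.** Let p be the per-subject probability of one given grade 3 event, and q = 1 − p. The documents give no rate, so p = 5%, 10% and 20% are assumptions. I calculate the chance of exactly one case, falling among the 4 (or 7) subjects, with no second case to trigger suspension.

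- Same rate in both cohorts, 8 + 11 = 19 treated: 4p·q^18.
- Same rate in both cohorts, 11 + 14 = 25 treated: 7p·q^24.
- Event confined to Cohort 2: 4p·q^7 (8 treated) and 7p·q^10 (11 treated).

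| Step and assumption | p = 5% | p = 10% | p = 20% |
|---|---|---|---|
| 2.0 million, equal rates | 0.20 × 0.397 = 8% | 0.40 × 0.150 = 6% | 0.80 × 0.018 = 1% |
| 3.0 million, equal rates | 0.35 × 0.292 = 10% | 0.70 × 0.080 = 6% | 1.40 × 0.0047 = 1% |
| 2.0 million, Cohort 2 only | 0.20 × 0.698 = 14% | 0.40 × 0.478 = 19% | 0.80 × 0.210 = 17% |
| 3.0 million, Cohort 2 only | 0.35 × 0.599 = 21% | 0.70 × 0.349 = 24% | 1.40 × 0.107 = 15% |

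The equal-rate figures fall as p rises because a second case, which does trigger suspension, becomes more likely.

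**The case against.** A reader might infer that nothing requires Cohort 2's data to be reviewed before these steps. The documents do not support that. The synopsis provides for ongoing review of clinical safety data with no cohort limit. The grade 3/4 rule is study-wide. Protocol 8.2.2 halts enrolment if an injected eye deteriorates significantly faster by ERG and BCVA. Sections 9.2 and 11.1 send adverse events to the sponsor and require notice to the IRB, and to the FDA as regulations require. These safeguards stand, but none is a review tied to a dose step. Post-injection ERG is scheduled only at months 6 and 12 (or early termination), and with no minimum interval in Cohort 2, escalation could come first.

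A reader might also infer that all 8 and 11 subjects are outside any gate. That overcounts. The gates are sequential and the 1.0 million step already considers the low-dose group.

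Nor do the documents show that the DSMB will not see Cohort 2 data. The synopsis speaks of safety data without limiting it to Cohort 1, and no DSMB charter is included. The content of the packages cannot be settled here. What can be said is that no text requires Cohort 2 data in them. Even a cumulative package could hold anywhere from none to all 8 Cohort 2 subjects at Cohort 1's 2.0 million review, and from none to all 11 at its 3.0 million review, depending on accrual.

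Three further points are fair. Having the advanced-disease cohort lead at each dose, with only the poorer eye injected, is a legitimate design; the fix keeps it. The rates above are assumed, and a lone grade 3 case is not the same as a missed hazard, since the sponsor receives every event. Finally, without a spacing rule a new listing may contain little follow-up on the latest subjects. It would still add information that the present gates do not ask for.

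**Conclusion.** The point holds in this form: the 2.0 and 3.0 million gates for Cohort 2 rest on Cohort 1 safety data, and no scheduled review of Cohort 2's own data is a condition of either. At full enrolment, 4 and 7 treated Cohort 2 subjects fall under no Cohort 2 gate, and only the general safeguards would catch a problem among them. The chance of a lone grade 3 case in that group runs from about 1% to 10% with equal rates, and from 14% to 24% if the event is confined to Cohort 2.

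These figures assume independent subjects, no grade 4 event, and that the low-dose group named at the 1.0 million step is Cohort 2's own. They treat low-dose events as apparent by that step; later-emerging ones would add to the gap. Who judges the low-dose group is also unstated, but that is missing detail and not part of this finding. Because the trial's primary objective is safety and the remedy is cheap, the gates should be changed.

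**What to change.** Amend the two gates in Protocol 3.1.2 and the matching synopsis text. Each step, to 2.0 and to 3.0 million, should require no unexpected safety issues both in Cohort 1 at that dose and in the Cohort 2 subjects already treated. The DSMB should judge this from a cumulative listing of both cohorts. If Cohort 2 subjects were treated after the last package, send the DSMB an updated listing and obtain its recommendation by correspondence before the step.

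The change adds no subjects, visits or spacing rule. The cost is slightly more work per package and possibly a short wait before at most two steps. SAP section 3 only restates the design, so editing it would change no escalation decision.

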3.2 Endpoints

3.2.1 Efficacy Endpoints

The response to jCell injection will be assessed based on the following:

- Change in BCVA at scheduled time points compared to baseline as well as contralateral eye. Acuity testing will be standardized using E-ETDRS.
- Changes in ellipsoid zone (EZ) band width at specified time points based on Spectral Domain Optical Coherence Tomography (OCT) compared to baseline as well as contralateral eye.
- Changes in electroretinogram (ERG) physiologic analysis compared to baseline as well as contralateral eye.
- Visual field sensitivity at scheduled time points post-treatment, using Goldmann visual field area and Humphrey 10-2, in subjects with adequate fixation to allow reliable testing.

In addition to the assessments listed above, a number of visual assessments that may be more appropriate for low vision subjects have been recommended by low vision experts. While BCVA is the gold standard for vision assessment, it is clear that this test is not particularly CONFIDENTIAL 16 of 41

relevant or accurate for subjects with very poor vision (legally blind). As there is little experience with our treatment approach, and subjects with very advanced vision loss are included in Cohort 1, it is planned to try some non-invasive assessments in subgroups of subjects, dependent upon the subjects' visual range and capabilities. These assessments include but are not limited to trial frame refraction, testing for contrast sensitivity (examples include Pelli-Robson Contrast Sensitivity Chart, Mars Letter Contrast Sensitivity Test, low luminance testing and mixed contrast eye charts); testing for color vision changes (e.g. D15 large caps, pseudoisochromatic plates), FrACT, California Central Visual Field Test, Tangent Screen Perimetry, ADL questionnaire (e.g. VFQ25, activity inventory, Low Vision Visual Functional Questionnaire [LF-VFQ], Function Independence Measures [FIM], Prosthetic Low Vision Rehabilitation [PVoVR]) and testing for changes in reading ability (e.g. Continuous Text Reading, MN Read). The goal of exploring some or all of these assessments is to develop a qualified, quantitative tool or set of tools for assessing post-treatment changes.

3.2.2 Safety Endpoints

The primary goal of the study is to evaluate the safety and tolerability of jCell injection: The criteria that will be used to establish safety include:

- Slit-lamp findings, i.e., anterior chamber cell or flare; acute cataract development or progression in phakic patients, vitreous haze.
- Absence of tumor formation, overt immune rejection, decrease in BCVA attributable to treatment
- Absence of clinically significant, persistent increase in intraocular pressure (>10 mm Hg above baseline or IOP > 25 mm Hg), clinically significant epiretinal membrane, retinal detachment, neovascularization, or endophthalmitis
- No clinically significant adverse events attributable to investigational product (jCell) injection
- Patient comfort (no intolerable pain related to procedure)

3.3 Study Duration

The overall duration of the study is anticipated to be approximately 2 years. The study will be considered to have started when the first site is initiated. The study will be considered to have finished after the last subject has completed the last follow-up visit in the study (12 months following treatment).

All subjects who receive jCell treatment will be closely monitored throughout the observation period. All subjects who receive treatment with jCell will be encouraged to participate in a follow-on study to assess potential long term effects (safety and efficacy) of jCell treatment. The follow-on study is planned to include an at least two years of additional subject monitoring; additional follow up visits will be scheduled at least every 6 months with

monitoring to include medical history and physical exam, vital signs, safety lab tests (as at other visits), urinalysis, adverse events, BCVA and slit lamp/fundus exam at each visit; and additional ophthalmic exams at specified visits. More frequent visits will be scheduled during the initial or follow-on study as appropriate should this be indicated by safety concerns.

3.4 Early Study Termination

The Sponsor may terminate this study at any time. Reasons for termination may include but are not limited to, the following:

- The incidence or severity of AEs in this or other studies point to a potential health hazard for study subjects.
- Insufficient subject enrollment.
- Any information becoming available during the study that substantially changes the expected benefit-risk profile of the investigational drug.

